1.1 Trial Description

This is a randomized, open-label Phase III non-inferiority trial to compare indicators of efficacy for MVA-BN[®] smallpox vaccine to ACAM2000[®] in 18-42 year old healthy vaccinia-naïve subjects.

A total of 440 vaccinia-naive subjects will be assigned randomly to two parallel treatment groups in a 1:1 ratio, 220 subjects in Group 1 and 220 subjects in Group 2.

Group 1:

One 0.5 ml standard dose MVA-BN[®] liquid-frozen vaccine contains a nominal titer of 1×10^8 tissue culture infectious dose 50% (TCID₅₀) Modified Vaccinia Ankara – Bavarian Nordic (MVA-BN[®]).

Two vaccinations each of 0.5 ml MVA-BN[®] vaccine will be administered four weeks apart (Day 0 and Day 28) as a subcutaneous (s.c.) injection in the non-dominant upper arm, followed by a single vaccination of ACAM2000[®] administered four weeks after the second MVA-BN[®] vaccination (Day 56). As per the prescribing information: one dose of reconstituted ACAM2000[®] vaccine consists of $2.5\text{-}12.5 \times 10^5$ plaque forming units of live vaccinia virus. A droplet (~ 0.0025 ml) vaccine is picked up with a bifurcated needle and is administered by the percutaneous route (scarification) using 15 jabs of the bifurcated needle.

Group 2:

A single vaccination of ACAM2000[®] will be administered at Day 0.

The active phase of the trial will begin at Day 0 (Visit 1) and continue through the second MVA-BN[®] vaccination (Day 56) and until 28 days after the ACAM2000[®] vaccination of Group 1 subjects (Visit 10). The active phase of the trial will begin at Day 0 (Visit 1) and continue until 28 days after the ACAM2000[®] vaccination of Group 2 subjects (Visit 4).

A remote Follow-up (FU) Visit by telephone or email is planned six months after the last trial vaccination. Only if there is a medical need, will the subject be asked to come back to the site or at the FU Visit (and specifically in the case of deployed military subjects) at another medical unit as agreed upon by the Principle Investigator.

The total duration (including screening period) is up to 22 weeks for Group 1 and up to 18 weeks for Group 2, plus remote correspondence (e.g. a phone call or email) six months after the last vaccination. If the remote correspondence reveals a medical need or any underlying condition that requires further examinations, the subject will be called in for a physical visit.

1.2 Objectives of the Trial

1.2.1 Co-Primary Objectives

To demonstrate the efficacy of MVA-BN[®] by assessing non-inferiority of MVA-BN[®] compared to ACAM2000[®] in terms of vaccinia-specific Plaque Reduction Neutralization Test (PRNT) antibody response at the Peak Visits (Day 42 for Group 1 and Day 28 for Group 2) and by showing that vaccination with MVA-BN[®] prior to administration of ACAM2000[®] results in an attenuation of take in terms of MLA.

1.2.2 Secondary Objectives

To assess non-inferiority of MVA-BN[®] compared to ACAM2000[®] in terms of vaccinia-specific Enzyme-linked Immunosorbent Assay (ELISA) antibody response at the Peak Visits.

To assess seroconversion rates of MVA-BN[®] compared to ACAM2000[®] at the Peak Visits.

To assess immune response dynamics in terms of antibody responses.

To assess the effect on the ACAM2000[®] vaccination take following MVA-BN[®] priming.

To assess and compare safety and reactogenicity of vaccinations with MVA-BN[®] and ACAM2000[®] given alone or ACAM2000[®] given after MVA-BN[®] priming.

1.3 Trial Population

Four hundred and forty (440) male and female volunteers from military personnel, aged 18 to 42 years who meet all of the inclusion and none of the exclusion criteria will be recruited for enrollment into this trial.

1.4 Endpoints

1.4.1 Co-Primary Endpoints

- PRNT GMT at the Peak Visits
- Maximum Lesion Area (MLA) in mm² after scarification with ACAM2000[®]

Both co-primary endpoint analyses will be conducted using the Per Protocol Set (PPS). However, identical secondary robustness analyses will also be conducted using the Full Analysis Set (FAS) and the Initially Seronegative Subset (ISS), a subset of the PPS.

1.4.2 Secondary Immunogenicity Endpoints

- GMTs at the Peak Visits measured by vaccinia-specific ELISA.
- GMTs at all antibody blood sample time points measured by vaccinia-specific PRNT and vaccinia-specific ELISA.

- PRNT seroconversion rates at Peak Visits defined as the percentage of initially seronegative subjects with appearance of antibody titers equal or greater than the ACV in a vaccinia-specific PRNT.
- ELISA seroconversion rates at Peak Visits defined as the percentage of initially seronegative subjects with appearance of antibody titers equal or greater than the ACV in a vaccinia-specific ELISA.

These secondary analyses will be conducted on the PPS, FAS and ISS.

1.4.3 Secondary Efficacy Endpoints

- Investigator assessed Maximum Lesion Diameter (MLD) in mm after scarification with ACAM2000[®]
- Investigator assessed Lesion diameter in mm at Day 6-8 after scarification with ACAM2000[®]
- Investigator assessed Lesion diameter in mm at Day 13-15 after scarification with ACAM2000[®]
- The individual take will be classified as either full or partial or absent by a blinded Independent Take Review Committee (ITRC), (see ITRC Charter Edition 3 dated 27-Feb-2015 for details).
- Lesion area in mm² at Day 6-8 after scarification with ACAM2000[®]
- Lesion area in mm² at Day 13-15 after scarification with ACAM2000[®]

(The correct measurement of the lesion area will be confirmed by a blinded ITRC).

These secondary analyses will be conducted on the PPS, FAS and ISS.

1.4.4 Safety and Reactogenicity Endpoints

- Occurrence, relationship to vaccine and intensity of any SAE.
- Occurrence of any cardiac sign or symptom indicating a case of myo-/pericarditis, i.e. AESI.
- Occurrence of any Grade 3 or 4 AE possibly, probably or definitely related to vaccine within 28 days after each vaccination.
- Occurrence, relationship to vaccine and intensity of any non-serious AEs within 28 days after each vaccination.
- Occurrence of solicited general AEs (body temperature, headache, myalgia, chills, nausea, fatigue, malaise, swollen lymph nodes) within 15 days after each vaccination (Days 0-14): Intensity, duration and relationship to vaccination.
- Occurrence of solicited local AEs (pain, redness (erythema), swelling, induration, itching (pruritus), and vaccination site appearance (normal/healed, red spot, bump, reddish blister

whitish blister, scab, ulcer/crater, warmth, swollen > 3inch, red streaks or drainage) within 15 days after each vaccination (Days 0-14): Intensity and duration.

- Daily measurement of lesion size, erythema and induration based on physical appearance of vaccination site as documented in the memory aid.
 - (i) major lesion diameter (mm) each day
 - (ii) major erythema diameter (mm) each day
 - (iii) major induration diameter (mm) each day

If the shape of the lesion, erythema (excludes lymphangitis) and induration observed is not round but rather asymmetrical then the largest (or major) cross-sectional measurement would be recorded.

The safety analyses will be conducted on the FAS.

1.5 Interim Analysis

No interim analysis is planned for this trial.

1.6 Data Safety Monitoring Board

The Data Safety Monitoring Committee (DSMB) is an independent expert panel appointed by the sponsor. This committee is in charge of surveying the subjects' safety throughout the course of the trial. All relevant roles, responsibilities and procedures for the DSMB are described in the DSMB charter. Since this is an open trial review will be done on unblinded summaries of the safety, disposition and demographic data prepared by the Chiltern biostatistician.

A summary of the activities and recommendations of the DSMB will be provided in the Clinical Study Report.

2 Trial Design

Table 1 Trial Procedure Schedule – Group 1

Visit (V)	SCR	V1	V2	V3	V4	V5	V6	V7	V8	V9	V10	Remote FU
Day / V +... d	-70--1	0	V1 +6-8	V1 +13-15	V1 +27-29	V4 +6-8	V4 +13-15	V1 +55-57	V7 +6-8	V7 +13-15	V7 +27-29	Last Vaccination +182-210
Week	-10--1	0	1	2	4	5	6	8	9	10	12	34-38
Procedures												
Informed consent	X											
Check inclusion / exclusion criteria	X	X										
Medical/Surgical History	X											
Check vaccination history and absence of vaccination scar	X											
Complete physical exam ¹	X											
Targeted physical exam ¹	X	X	(X)	X	X	(X)	X	X	(X)	X	X	(X)
Evaluation of vital signs	X	X	X	X	X	X	X	X	X	X	X	(X)
Recording of Baseline signs and symptoms	X	X										
Check cardiac risk factors	X											
ECG ²	X			X			(X)			X		
Questions on cardiac signs and symptoms		X		X	X		X	X		X	X	
Review of prior/concomitant medications	X	X		X	X		X	X		X	X	(X)
Counseling ³	X	X	X	X	X	X	X	X	X	X	X	
Examination of vaccination site		X	X	X	X	X	X	X	X	X	X	
Photo of vaccination site									X	X		
Bandage application / change ⁴								X	X	X		
Assessment of axillary and supraclavicular lymphadenopathy		X	X	X	X	X	X	X	X	X	X	
SAE/AE/AESI recording		X	X	X	X	X	X	X	X	X	X	X ⁵

Trial Procedure Schedule – Group 1 continued

Visit (V)	SCR	V1	V2	V3	V4	V5	V6	V7	V8	V9	V10	Remote FU
Day / V + ... d	-70 -1	0	V1 +6-8	V1 +13-15	V1 +27-29	V4 +6-8	V4 +13-15	V1 +55-57	V7 +6-8	V7 +13-15	V7 +27-29	Last Vaccination +182-210
Week	-10 -1	0	1	2	4	5	6	8	9	10	12	34-38
Vaccination												
Randomization		X										
Vaccine administration		X			X			X				
Subject Observation (at least 30 minutes)		X			X			X				
Handout of memory aid ⁶		X			X			X		X ⁷		
Review of memory aid			X	X		X	X		X	X	X ⁷	
Collection of memory aid ⁶				X			X			X	X ⁷	
Labs												
Pregnancy test ⁸	X	X			X			X			X	
Safety lab ²												
(CBC with differential, total bilirubin, Alk Phos, AST, ALT, creatinine, sodium, potassium and calcium)	X			X			X			X		(X)
Total, HDL and LDL cholesterol	X											
Hepatitis serology (HBsAg / Anti-HCV)	X											
HIV	X											
Troponin I testing ²	X			X						X		
Blood draw for antibody analysis		X	X	X	X		X	X			X	
Blood volume												
Blood volume drawn per visit (ml) ⁹	22	21	16	26	21		26	21		10	21	(10)
Cumulative blood volume drawn (ml) ⁹	22	43	59	85	106		132	153		163	184	(194)

- () Only indicated in case of medical need or any underlying condition that requires further examinations.
- 1 For more information on the physical examinations, please refer to Section 8.2.3 of the CTP.
 - 2 Additional safety measures can be taken at any other trial visits or at unscheduled visits, if clinically indicated.
 - 3 Counseling on avoidance of pregnancy and HIV infection and specifically after the ACAM2000[®] vaccination counseling on the avoidance of contact spread. At Visit 10 counseling for avoidance of pregnancy is not required.
 - 4 After ACAM2000[®] administration subjects should change their own dressings as instructed by the administering clinic (leave the bandage on for the 1st 48 hours, then change every day or when bandage becomes wet) using the Care Kits provided by site staff until the vaccination site scab falls off, as this will keep the vaccination site intact and will minimize softening. Salves or ointments must not be applied to the vaccination site. Measurements of the vaccination site are to be taken until bandage not required.
 - 5 Follow-up on ongoing AEs, AESIs, SAEs and recording of new SAEs/AESIs.
 - 6 The memory aid should be completed daily for 15 days (day of vaccination and the following 14 days). If symptoms persist at 14 days post vaccination, temperature/symptom should be recorded until resolution or Visit 10.
 - 7 If lesion at vaccination site has not healed at Day 14, measurements of lesion size, erythema and induration should be recorded on a memory aid extension each day until healed or Visit 10.
 - 8 WOCBP only. At Screening Visit, a serum test must be performed. At all other visits, either a serum or urine pregnancy test will be performed.
 - 9 Approximate volumes of single blood draws: Safety lab including all tests: 22 ml at SCR (including serum for pregnancy test) and 10 ml at regular visits, 5 ml for serum pregnancy test and 16 ml for antibody analysis.

Table 2 Trial Procedure Schedule – Group 2

Visit (V)	SCR	V1	V2	V3	V4	V5	V6	Remote FU
Day / V + ... d	-70- -1	0	V1 +6-8	V1 +13-15	V1 +27-29	V1 +41-43	V1 +55-57	Last Vaccination +182-210
Week	-10- -1	0	1	2	4	6	8	26-30
Procedures								
Informed consent	X							
Check inclusion / exclusion criteria	X	X						
Medical/Surgical History	X							
Check vaccination history and absence of vaccination scar	X							
Complete physical exam ¹	X							
Targeted physical exam ¹	X	X	(X)	X	X			(X)
Evaluation of vital signs	X	X	X	X	X			(X)
Recording of Baseline signs and symptoms	X	X						
Check cardiac risk factors	X							
ECG ²	X			X				
Questions on cardiac signs and symptoms		X		X	X			
Review of prior/concomitant medications	X	X		X	X			(X)
Counseling ³	X	X	X	X	X			
Examination of vaccination site		X	X	X	X			
Photo of vaccination site ⁴		X	X	X				
Bandage application / change ⁴		X	X	X	X			
Assessment of axillary and supraclavicular lymphadenopathy		X	X	X	X			
SAE/AE/AESI recording		X	X	X	X			X ⁵

Trial Procedure Schedule – Group 2 continued

Visit (V)	SCR	V1	V2	V3	V4	V5	V6	Remote FU
Day / V + ... d	-70 -1	0	V1 +6-8	V1 +13-15	V1 +27-29	V1 +41-43	V1 +55-57	Last Vaccination +182-210
Week	-10 -1	0	1	2	4	6	8	26-30
Vaccination								
Randomization		X						
Vaccine administration		X						
Subject Observation (at least 30 minutes)		X						
Handout of memory aid ⁶		X		X ⁷				
Review of memory aid			X	X	X ⁷			
Collection of memory aid ⁶				X	X ⁷			
Labs								
Pregnancy test ⁸	X	X			X			
Safety lab ²								
(CBC with differential, total bilirubin, Alk Phos, AST, ALT, creatinine, sodium, potassium and calcium)	X			X				(X)
Total, HDL and LDL cholesterol	X							
Hepatitis serology (HBsAg / Anti-HCV)	X							
HIV	X							
Troponin I testing ²	X			X				
Blood draw for antibody analysis		X	X	X	X	X	X	
Blood volume								
Blood volume drawn per visit (ml) ⁹	22	21	16	26	21	16	16	(10)
Cumulative blood volume drawn (ml) ⁹	22	43	59	85	106	122	138	(148)

- () Only indicated in case of medical need or any underlying condition that requires further examinations.
- 1 For more information on the physical examinations, please refer to Section 8.2.3 of the CTP.
 - 2 Additional safety measures can be taken at any other trial visits or at unscheduled visits, if clinically indicated.
 - 3 Counseling on avoidance of pregnancy and HIV infection and specifically after the ACAM2000[®] vaccination counseling on the avoidance of contact spread. At Visit 10 counseling for avoidance of pregnancy is not required.
 - 4 After ACAM2000[®] administration subjects should change their own dressings as instructed by the administering clinic (leave the bandage on for the 1st 48 hours, then change every day or when bandage becomes wet) using the Care Kits provided by site staff until the vaccination site scab falls off, as this will keep the vaccination site intact and will minimize softening. Salves or ointments must not be applied to the vaccination site. Measurements of the vaccination site are to be taken until bandage not required.
 - 5 Follow-up on ongoing AEs, AESIs, SAEs and recording of new SAEs/AESIs.
 - 6 The memory aid should be completed daily for 15 days (day of vaccination and the following 14 days). If symptoms persist 14 days post vaccination, temperature/symptom should be recorded until resolution or Visit 4.
 - 7 If lesion at vaccination site has not healed at Day 14, measurements of lesion size, erythema and induration should be recorded on a memory aid extension each day until healed or Visit 4.
 - 8 WOCBP only. At Screening Visit, a serum test must be performed. At all other visits, either a serum or urine pregnancy test will be performed.
 - 9 Approximate volumes of single blood draws: Safety lab including all tests: 22 ml at SCR (including serum for pregnancy test) and 10 ml at regular visits, 5 ml for serum pregnancy test and 16 ml for antibody analysis.

3 Statistical Methods and Considerations

3.1 Randomization Procedure

Target enrollment in the trial is 440 subjects to be vaccinated (220 subjects in Group 1 and 220 subjects in Group 2). Randomized treatment assignments for the subjects will be done after confirmation of subject's eligibility. Subjects will be allocated randomly into either Group 1 or Group 2 across the one clinical trial site in a 1:1 ratio. There will not be any stratification factors used in the randomization.

3.2 Immunogenicity Co-Primary Trial Hypothesis

Both co-primary trial hypotheses will be conducted on the PPS as the main analysis set. Similar analyses will also be conducted on the FAS and ISS.

The immunogenicity co-primary objective of the trial is to assess non-inferiority of MVA-BN[®] compared to ACAM2000[®] in terms of vaccinia-specific PRNT antibody response at the Peak Visits (Day 42 for Group 1 and Day 28 for Group 2).

It is assumed that the \log_{10} titers for the PRNT are normally distributed with a mean of m_1 in Group 1 and a mean of m_2 in Group 2 and a common standard deviation (SD) for both groups.

The trial should demonstrate that the Day 42 GMT of Group 1 is not lower than the Day 28 GMT of Group 2 by more than a pre-specified amount. This amount is called the non-inferiority margin (Δ).

The test of non-inferiority will be applied for the following hypothesis:

$H_0: m_1 - m_2 \leq -\Delta$ versus $H_1: m_1 - m_2 > -\Delta$, where

Δ is the non-inferiority margin and is chosen in this trial as 0.301 on the \log_{10} titers (i.e. a factor of $\frac{1}{2}$ reported on the original titer scale).

Specifically, a standard homoscedastic one sided 97.5% lower confidence limit (LCL) of the difference between the log PRNT averages of the two groups will be calculated (Group 1 – Group 2). If the LCL is above $-\Delta$ then the null hypothesis will be rejected and the non-inferiority of MVA-BN[®] to ACAM2000[®] will have been demonstrated.

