## 2.6.2 Immunogenicity Overview of MVA-BN®

In three Phase I and II dose finding trials MVA-BN® was tested for safety and immunogenicity among healthy volunteers (Vollmar, 2006; Frey, 2007; Von Krempelhuber, 2010; Zitzmann-Roth, 2015). Across these trials a linear dose relationship was observed between the vaccine doses for both ELISA and PRNT titers. Maximum ELISA seroconversion rates and peak titers were reached two weeks after the second vaccination, with 100% seroconversion after the second dose for all dose groups receiving at least  $2 \times 10^7$  TCID50 of MVA-BN® or higher. Statistical analysis indicated lower doses to be inferior to a nominal titer of  $1 \times 10^8$  TCID50 tested throughout all dose ranging studies. This highest dose tested achieved ELISA seroconversion rates between 81 and 100% already after the first dose. For the PRNT, the same trend was observed with 71-96% seroconversion rates two weeks after the second MVA-BN® administration in all groups receiving the highest dose.

The early onset of seroconversion and the higher titers of total and neutralizing antibodies combined with an excellent safety profile qualified the highest dose as the most suitable human dose. Therefore, based on the results of these dose ranging studies, coupled with the animal immunogenicity and efficacy studies, the final optimal (standard) dose and schedule for the general population was decided to be two doses of MVA-BN® with a nominal titer of  $1 \times 10^8$  TCID50 administered (s.c.) four weeks apart.

Although antibody responses measured by ELISA in HIV infected subjects tend to be lower compared to GMT in healthy (Greenberg, 2013; Overton, 2015) and AD subjects four weeks after the first and second vaccinations with MVA-BN®, GMTs measured by PRNT were comparable in HIV infected compared to healthy and AD populations (von Sonnenburg, 2014; Greenberg, 2015). The ability of the second MVA-BN® vaccination to significantly boost the immune response in immunocompromised populations to high titer levels is as robust as in the healthy population.

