### 12.1 Mechanism of Action

Vaccinia virus is a member of the same taxonomic group (the Orthopox genus) as smallpox (variola) virus, and immunity induced by vaccinia virus cross-protects against variola virus. Vaccinia virus causes a localized virus infection of the epidermis at the site of inoculation, surrounding dermal and subcutaneous tissues, and draining lymph nodes. Virus may be transiently present in blood and infects reticuloendothelial and other tissues. Langerhans cells in the epidermis are specific targets for the early stage of virus replication. The formation of a pustule ('pock' or 'take') at the site of inoculation provides evidence of protective immunity. The virus replicates within cells and viral antigens are presented to the immune system. Neutralizing antibodies and B and T cells provide long-term memory. The level of neutralizing antibody that protects against smallpox is unknown but >95% of persons undergoing primary vaccination develop neutralizing or hemagglutination inhibiting antibodies to vaccinia.

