3.6.1 Immunogenicity Co-Primary Endpoint

The immunogenicity co-primary objective of the trial is to demonstrate the non-inferiority of MVA-BN[®] to a conventional smallpox vaccine (ACAM2000[®]) in terms of PRNT antibody response (GMTs) at the Peak Visit. Hence the following sample size calculation was performed for the co-primary immunogenicity endpoint.

Assuming a standard significance level alpha of 5%, a power of $\geq 90\%$ and the same expected individual peak PRNT GMTs in the MVA-BN[®] group (Group 1) and the ACAM2000[®] group (Group 2), then the only remaining parameter is the SD of the \log_{10} titers.

As a basis for calculation, the combined calculated value of the SD at Day 42 of the \log_{10} titers for healthy vaccinia-naïve subjects who received the standard MVA-BN[®] vaccination schedule was taken from three Phase II MVA-BN[®] studies (POX-MVA-005, POX-MVA-008 and POX-MVA-011). In total this was 419 healthy subjects and the calculated SD is 0.807 with a 95% confidence interval of (0.756, 0.866).

Adopting a worst case scenario and using the upper limit of the confidence interval, i.e. assuming $SD = 0.866$, this yields a required sample size for this trial of 175 in the PPS in both groups.

In order to account for an estimated 20% rate for exclusion from the PPS (verbal communication from USAMRIID as experience from their trials in this population), a total of 220 subjects will be recruited into each of the groups.

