3.7.3 Initially Seronegative Subset

As seen in supposedly vaccinia-naive populations in previous MVA-BN[®] trials, some subjects will most likely be initially tested seropositive at Visit 1 prior to vaccination in either the ELISA or PRNT. An additional subgroup analysis based on the subset of the PPS of initially seronegative subjects, the Initially Seronegative Subset (ISS) will therefore be performed which will provide assurances that the results have not been affected by the possible inclusion of some vaccinia-experienced subjects. In doing so it should be noted that some of the initially seropositive values might be false positive values. However, there is no reliable way to determine which seropositive cases are false positive and which are true positive values, and the ISS is therefore a conservative approach to validating the results in a confirmed naïve population.

A subject of the PPS will be part of the ISS, if the subject is seronegative for both ELISA and PRNT at baseline.

The ISS population will be used as an additional robustness analysis set for the immunogenicity and the demographic analyses.

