3.10.7 Immunogenicity Analysis

The co-primary immunogenicity objective of the trial is to assess non-inferiority of MVA-BN[®] compared to ACAM2000[®] in terms of PRNT antibody response at the Peak Visits (Day 42 for Group 1 and Day 28 for Group 2).

Suppose m_1 is the PRNT \log_{10} titer mean in Group 1 and m_2 is the PRNT \log_{10} titer mean in Group 2. The test of non-inferiority will be applied for the following hypothesis:

$$H_0: m_1 - m_2 \leq -\Delta \text{ versus } H_1: m_1 - m_2 > -\Delta \text{ where}$$

Δ is the non-inferiority margin. For the PRNT the non-inferiority margin will be 0.301 on the \log_{10} scale which is equivalent to a doubling on the original titer scale for the GMT. This is the same Δ for the PRNT as was used for the assessment of non-inferiority of ACAM2000[®] to Dryvax[®] (ACAM2000 VRBPAC Briefing Document, April 2007).

The above hypotheses will be tested for the PRNT using a t-test on the difference of the two means based on the assumption that the \log_{10} titers are normally distributed (which has been the case in all previous MVA-BN[®] studies). Specifically, a one-sided 97.5% confidence interval for the difference of the \log_{10} titer means (based on the assumption of a common standard deviation [SD]) will be calculated. If the lower limit of this confidence interval is greater than $-\Delta$, then the null hypothesis will be rejected and non-inferiority of MVA-BN[®] to ACAM2000[®] will have been demonstrated.

For better interpretation the primary analysis will be presented in terms of the ratio of the GMTs, which is equivalent to taking the antilog of the differences in the \log_{10} means. Similarly the corresponding confidence intervals are presented on the original titer scale by taking the antilog of the CIs calculated on the \log_{10} scales. In this way, non-inferiority of MVA-BN[®] to ACAM2000[®] will be demonstrated if the lower limit of CI of the ratio of the GMTs lies within the interval above $\frac{1}{2}$. This interval is obtained as the antilog of the $-\Delta$.

A similar analysis will be conducted for descriptive purposes on the ELISA \log_{10} titer means. This will be done as secondary endpoint. The non-inferiority margin is chosen to be 0.176 for the ELISA on the \log_{10} scale (which is equivalent to a factor of $\frac{2}{3}$ on the original titer scale for the GMT).

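### The PRNT non-inferiority limit pools variances on an unsupported common SD; if Group 1 has both the larger SD and the smaller Per Protocol Set, its one-sided error modestly exceeds 2.5%

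*SAP*

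**What the plan says.** SAP 3.2 assumes normal log10 PRNT titers with "a common standard deviation (SD) for both groups" and bases the decision on "a standard homoscedastic one sided 97.5% lower confidence limit (LCL) of the difference between the log PRNT averages of the two groups". SAP 3.10.7 and Protocol 9.2.1 describe the same t-test: "a one-sided 97.5% confidence interval for the difference of the" log10 means, assuming one SD. Non-inferiority is declared if the limit lies above -0.301. There are no covariates. The analysis is repeated on the Full Analysis Set (FAS) and the Initially Seronegative Subset (ISS), but no unequal-variance version is planned on any set.

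The SD used for sizing is 0.807 (95% CI 0.756 to 0.866), from 419 MVA-BN recipients in three Phase II trials (SAP 3.6.1). The upper limit, 0.866, is used. SAP 3.6.1 assumes about 20% exclusion from the PPS in each group. SAP 3.7.2, however, asks Group 1 for three vaccinations and all visits to Visit 10 (week 12), and Group 2 for one vaccination and visits to Visit 4 (week 4).

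**The concern.** When two groups differ in both variance and size, the pooled standard error gives too much weight to the larger group's variance. If the smaller group is the more variable one, the interval is too narrow, and here the error favours declaring non-inferiority.

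The plan gives some reason to expect that combination.

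- **Size.** Only Group 1 subjects can lose PPS status by missing a second or third vaccination, and they have eight more weeks of visits to complete.
- **Spread.** Protocol 2.6.2 reports: "For the PRNT, the same trend was observed with 71-96% seroconversion rates two weeks after the second MVA-BN" administration. The ACAM2000 label in Protocol Appendix IVc (label section 12.1) says that more than 95% of "persons undergoing primary vaccination develop neutralizing or hemagglutination inhibiting antibodies to vaccinia". Titers below the assay cut-off are set to 1, so each non-responder enters at log10 = 0, and more non-responders generally means a larger SD.

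This limit alone decides one of the two co-primary endpoints. For the lesion-area co-primary, SAP 3.5 adds a supportive Price-Bonett analysis in case the homogeneity assumption fails. PRNT has no such check.

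**Working it through.** **The plan's own figure.** Inputs from SAP 3.2 and 3.6.1: margin 0.301, SD 0.866, true difference 0, one-sided 2.5%, power 90%.

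n = 2 × (1.96 + 1.2816)² × 0.866² / 0.301² = 173.96, so 174 by the normal approximation. The noncentral-t power at 175 per group is 90.0%, so 175 is right. A one-sided 5% level would give 142, which confirms that the design is one-sided 2.5%. 175/0.8 = 218.75, against 220 planned.

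**A Group 2 SD.** None is given in the sponsor's assay. An indirect value comes from Study 1 in the label (section 14, Table 4), where the GMTs were 166 (n = 565) and 255 (n = 190) and the lower limit was -0.307:

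- difference = log10(166/255) = -0.186
- SE = (-0.186 + 0.307)/1.96 = 0.0615
- SD = 0.0615 / √(1/565 + 1/190) = 0.73

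This is another trial, and the figure pools ACAM2000 with Dryvax. The value 0.6 used below is purely an assumption.

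**Error rate of the pooled limit at a true difference of -0.301.**

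- s_p² = [(n1 - 1)s1² + (n2 - 1)s2²] / (n1 + n2 - 2)
- SE_pooled = s_p √(1/n1 + 1/n2)
- SE_true = √(s1²/n1 + s2²/n2)
- error = 1 - Φ(1.96 × SE_pooled / SE_true)

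Example with SDs 0.866 and 0.73 and PPS 154/198:

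- s_p² = (153 × 0.750 + 197 × 0.533)/350 = 0.628, so s_p = 0.792
- SE_pooled = 0.0851 and SE_true = 0.0870, ratio 0.979
- error = 1 - Φ(1.919) = 2.75%

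| PPS, Group 1/Group 2 (assumed) | Loss from 220 | 0.807 vs 0.73 | 0.866 vs 0.73 | 0.866 vs 0.6 |
|---|---|---|---|---|
| 175/175 | 20% / 20% | 2.50% | 2.50% | 2.50% |
| 165/198 | 25% / 10% | 2.61% | 2.68% | 2.88% |
| 154/198 | 30% / 10% | 2.65% | 2.75% | 3.04% |
| 140/205 | 36% / 7% | 2.72% | 2.88% | 3.33% |
| 198/154 (reversed) | 10% / 30% | 2.36% | 2.26% | 2.03% |

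Simulation with normal data (200,000 runs) agrees. At 154/198 with 0.866 vs 0.73 the pooled limit gives 2.76% and Welch 2.52%; with 0.866 vs 0.6 they give 2.99% and 2.45%.

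**Effect of the spike at log10 = 0.** Assume responders with mean 2.0 and SD 0.45, and non-response of 15% in Group 1 and 5% in Group 2 (overall SDs 0.83 and 0.62). At 154/198 the formula gives 2.9%. Simulation gives about 3.1 to 3.2% for the pooled limit and 2.8 to 2.9% for Welch. At 175/175 both give 2.6%. That remainder is skewness, which Welch does not cure. With 4% against 5% non-response (SDs 0.59 and 0.62) at 154/198, the pooled limit gives 2.4% and Welch 2.6%, so at the top of the 71-96% range there is no inflation of the pooled limit.

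**Power with Welch (normal approximation).** 90.2% at 175/175 and 89.9% at 154/198 with SD 0.866 in both groups; 93.3% at 154/198 with 0.866 and 0.73.

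**The case against.** The strongest reply is that neither premise is shown.

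- **Larger Group 1 spread.** The 71-96% is seroconversion in the sponsor's development trials. The label's figure of more than 95% covers live vaccinia vaccination generally and, in section 12.1, counts hemagglutination-inhibiting antibody too. Neither describes ACAM2000 in the sponsor's PRNT, and label section 12.2.2 itself calls titers highly variable. This stands: the larger Group 1 variance is a cross-assay inference.
- **Smaller Group 1 PPS.** The plan allows the same 20% loss in both groups, citing experience in this population. The heavier Group 1 requirements are real, but the size of any gap is assumed. In every unequal split with the smaller Group 1 shown above, Group 1 misses its target of 175.
- **Repeat analyses.** The FAS does not require completion to Visit 10, so its group sizes should be closer. But subjects withdrawn after the first MVA-BN dose skip Visit 6 (Protocol 4.2.5) and so have no Day 42 titer, and nothing is imputed (SAP 3.8.1). The FAS is also not the confirmatory set, and it uses the same kind of interval.
- **Baseline titers.** SAP 3.7.3 expects that "some subjects will most likely be initially tested seropositive at Visit 1 prior to vaccination" and answers with the ISS analysis, so baseline serostatus is not ignored.

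What survives is an untested assumption in a decisive analysis, with a near-free remedy.

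A reader might infer an error rate near 3.7%. That needs, for example, 29% non-response with responder mean 2.0 and SD 0.5, which implies a Group 1 SD of 1.00, against 0.60 in Group 2 (3% non-response) and a 140/205 split. An SD of 1.00 lies outside the documented interval of 0.756 to 0.866, so the documents do not support that figure.

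**Conclusion.** The point holds as a modest robustness weakness. If Group 1 has both the larger SD and the smaller PPS, the nominal 2.5% becomes about 2.6 to 2.9% with Group 1 SDs inside the documented interval against 0.73, or about 3.0 to 3.3% with 0.866 against 0.6 at splits of 154/198 to 140/205. Both conditions are needed. Unequal SDs alone do nothing at equal PPS sizes, and the reversed imbalance makes the test conservative. The PPS splits and the Group 2 SDs are assumptions. The documents establish only that the common SD has no ACAM2000 support in this assay and that the PPS rules are heavier for Group 1.

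Two further inferences should be resisted. The sample size is not in error: 175 per group gives 90.0% power under the stated inputs. And covariate adjustment is not a remedy for the error rate. It could add precision, but by an unknown and probably small amount: subjects are vaccinia-naive by eligibility, so most baseline PRNT values should sit at log10 = 0, and the documents give no R-squared.

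**What to change.** In SAP 3.2 and 3.10.7 and Protocol 9.2.1, before database lock, define the primary limit as the Welch one-sided 97.5% lower limit: the difference in mean log10 titers minus t(0.975, Satterthwaite df) × √(s1²/n1 + s2²/n2). Keep the pooled limit as a prespecified sensitivity analysis, and report the SD and n of each group beside both. Apply the same change to the FAS and ISS repeats. Margin and sample size are unchanged.

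This removes most of the inflation, though not the part due to skewness from titers set to 1. It also settles in advance which limit decides if the two fall on opposite sides of -0.301.

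The cost is a wording amendment and a few lines of code, with no new data and negligible loss of power. Prespecified adjustment for baseline log10 PRNT, age and sex may be added as a separate, optional precision measure.
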